8.2.2. Derived and Transformed Data

Data will not be derived or transformed except the necessary calculation for end points based on data collected in CRF. Regarding the outliers, queries will be raised to data manager and they should be resolved or confirmed before database lock.

8.3. Study Population

8.3.1. Patient Disposition

A disposition of all enrolled patients will be summarized. The number and percentage of patients discontinuing from the study and the primary reason for discontinuation will be summarized.

8.3.2. Protocol Deviation

Major protocol deviations will be categorized by deviation type (e.g. Entry/eligibility, use of excluded medication). The subject incidence of major protocol deviations will be summarized overall and by deviation category. All major protocol deviations will be presented in a listing as well.

8.3.3. Demographic

Patient demographics and baseline characteristics will be summarized for the mITT population. Descriptive statistics will be provided for age, height, weight, and body mass index (BMI). Frequencies and percentages will be tabulated for sex, ethnicity, and Eastern Cooperative Oncology Group (ECOG) performance status (PS) score.

8.3.4. Medical History

Medical history will be summarized by primary system organ class (SOC) and preferred term (PT). Medical history will be coded using Medical Dictionary for Regulatory Activities (MedDRA, Version 25.0 or higher) terminology. Frequencies and percentages will be tabulated for medical history by SOC and PT.

8.3.5. Transplant History

Transplant history will be summarized for:

- Auto-transplant (Yes/No)
- Auto-transplant number
- Indication for transplant
- Allo-transplant number
- HLA match (matched, unmatched)
- Stem cell type (bone marrow, peripheral blood, bone marrow + peripheral blood, cord blood)
- Donor source (related, unrelated)
- Conditioning regimen (myeloablative, nonmyeloablative)
- Donor age
- Donor gender
- Donor CMV serostatus
- Recipient CMV serostatus
- Prophylaxis for GVHD

8.3.6. GVHD History

The baseline characteristics of GVHD will be summarized for:

- Prior aGVHD
- Time from transplant to cGVHD diagnosis
- Time from cGVHD diagnosis to enrollment
- Time from transplant to enrollment
- cGVHD severity: mild / moderate / severe
- Number of organs involved at baseline
- Organ involvement at baseline per NIH criteria

8.3.7. Prior Therapies for cGVHD

Prior therapies for cGVHD will be summarized for:

Number of prior lines of systemic cGVHD therapy

Prior systemic cGVHD therapies

Best response to the recent systemic therapy

8.3.8. Treatment Compliance and Exposure

Treatment compliance and exposure will be analyzed on mITT population.

Duration of treatment and duration of follow up will be summarized as a continuous variable and also categorically by numbers and percentages for each category (0-3 months, 3-6 months, 6-9 months, >9 months).

Descriptive summary statistics of cumulative exposure (patient year), actual cumulative dose (mg), ADI (mg/day), RDI (%) and RDI as a categorical endpoint (>95%, ≤95%) will be presented.

Number and percentage of patients for each RDI category (<80%, 80-100%, >100%) will be summarized by visit.

Number and percentage of patients with dose reduction and dose interruption will be summarized.

8.4. Efficacy Analyses

Analyses for primary endpoint will be based on mITT and PPS. Other efficacy analyses will be based on mITT unless otherwise specified.

8.4.1. Analyses for Primary Endpoints

ORR (%) = *(the number of patients with a best response meeting the criteria of CR or PR at any post-baseline response assessment / the total number of patients in the analysis set)*

*100%.

ORR will be calculated based on mITT and PPS. Point estimate and 95% confidence interval and 97.5% confidence interval (Clopper-Pearson (exact) method and Normal Approximation method) of ORR will be provided.

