All comorbid medications or treatments will be documented during the study period. Initiation of new systemic cGVHD treatment will be considered as starting a new cGVHD treatment and will be considered a failure of BN101/belumosudil treatment.

- Transient increases in corticosteroid dose (no more than 1 mg/kg/day of prednisone equivalent) for treatment of cGVHD episodes will be permitted during the study treatment period, provided that the dose is reduced to pre-enrollment levels within 6 weeks. If the dose remained elevated for more than 6 weeks, it was considered a BN101/belumosudil treatment failure. More than 2 episodes of cGVHD requiring an increase in the dose of corticosteroid therapy within the first 6 months of BN101/belumosudil treatment will also be considered a BN101/belumosudil treatment failure.
- Continuation of treatment with calcineurin phosphatase inhibitors (e.g., tacrolimus, cyclosporine), sirolimus, MMF, methotrexate, azathioprine, or extracorporeal photochemistry (ECP), which have been stabilized at baseline, is permitted during study treatment.
 - Local/organ-specific therapy for cGVHD is allowed during study treatment.
- During study treatment, CYP3A4 inducers (e.g., rifampin, phenobarbital) are prohibited, proton pump inhibitors (e.g., rabeprazole, omeprazole) are permitted for short

Concomitant medication and concomitant therapy

	periods of time only (no more than 1 week), and CYP1A2 inhibitors/inducers, CYP3A4
	inhibitors, drugs that prolong the QT/QTc interval should be used with caution (see Appendix for details of CYP3A4 and CYP1A2 inhibitors/inducers, and drugs that prolong the QT/QTc
	interval).
	- The use of other systemic therapies for cGVHD (including rituximab, ruxolitinib,
	ibrutinib, etc.) or other clinical trial medications is prohibited during study treatment.
	- Tobacco, alcohol, and caffeinated beverages or foods are prohibited on the day of PK sample collection.
	The primary efficacy endpoint was the Overall Response Rate (ORR, including
	Complete Response [CR] and Partial Response [PR]), assessed according to the NIH consensus criteria (2014).
Efficacy endpoints	Secondary efficacy endpoints included median Duration of Response (DOR), Change in Lee Symptom Scale Score, Response rate by organ system, Percentage of subjects with best efficacy as PR and percentage of subjects with best efficacy as CR, Change in

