Data lock and primary analysis will be performed 6 months after enrollment of the last subject. All subjects will continue to be followed up for an additional 6 months after the primary analysis as required by the protocol, i.e., the study will end 12 months after enrollment of the last subject, and a follow-up analysis will be performed at the end of the study. Subjects who have not yet experienced cGVHD progression at the end of the study, and in the judgment of the investigator, the benefits of continued dosing outweigh the risks, the sponsor will continue to provide BN101/belumosudil medication at no cost until cGVHD progression, intolerable toxicity, initiation of a new cGVHD therapy, recurrence of hematological neoplasm, loss to follow-up, withdrawal of consent, or death, etc., whichever occurred first.

Serious adverse events (SAEs), study drug use, and subject survival will continue to be collected for subjects who continue to be free of charge while the study drug, BN101/belumosudil, is administered at the end of the study.

Subjects who have not terminated BN101/belumosudil treatment at the end of the main study will

have a uniform end-of-treatment visit at the end of the main study.

AEs that remain at the end-of-treatment visit will be subject to continued follow-up, and all SAEs and AEs related to study treatment will be subject to follow-up until the event is resolved and the investigator considers the event to be stabilized or irreversible.

Twelve subjects at the designated centers will receive dense PK blood collection and the remaining subjects will receive sparse PK blood collection.

The primary efficacy endpoint of the study was ORR, defined as the proportion of subjects evaluated as CR or PR according to the NIH Consensus Criteria (2014) at any one post-baseline assessment. Secondary efficacy endpoints included median Duration of Response (DOR), Change in Lee Symptom Scale Score, Response rate by organ system, Percentage of subjects with best efficacy as PR and percentage of subjects with best efficacy as CR, Change in corticosteroid dose, Change in CNI dose, Failure-Free Survival (FFS), Overall Survival (OS), Change in cGVHD severity based on the Physician-Reported Global cGVHD Activity Assessment, and Change in symptom activity based on cGVHD Activity Assessment Patient Self-Report.

Changes in the PROMIS Physical Psychological Functioning Global Health Score will be analyzed as an exploratory endpoint of this study.

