6.4.1 Corticosteroids

Therapeutic doses of corticosteroids are to be collected throughout the study. After ≥2 weeks of BN101/belumosudil use, the dose of corticosteroids may be reduced at the discretion of the investigator.

A transient increase in corticosteroid dose (no more than 1 mg/kg/day prednisone equivalent) is permitted during cGVHD episodes, but this dose must be adjusted to the pre-enrollment dose level within 6 weeks. If the dose remains elevated for more than 6 weeks, it will be considered a BN101/belumosudil treatment failure. The occurrence of more than 2 episodes of cGVHD requiring an increase in corticosteroid dose during the first 6 months of BN101/belumosudil treatment will also be considered a BN101/belumosudil treatment failure.

If the planned response assessment falls during a cGVHD episode of treatment, this response assessment will still be performed as planned, but the assessment will not be included in the primary efficacy analysis.

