5.1. Efficacy Endpoints

5.1.1. Primary Efficacy Endpoints

The primary efficacy endpoint is the overall response rate (ORR) as assessed by the investigators based upon the 2014 NIH Consensus Development Project on Clinical Trials in cGVHD.

Response is assessed using individual scores from ten systems (Skin, Eyes, Mouth, Esophagus, Upper GI, Lower GI, Liver, Lungs, Joints and Fascia and Global Severity Rating (GSR)). Response is assessed with respect to the baseline (Cycle 1, Day 1 (C1D1)) cGVHD assessment. The overall response at each assessment time point will be categorized as Complete Response (CR), Partial Response (PR), or Lack of Response (LR), where LR includes the response status of unchanged, mixed, or progression as defined in [Table 1](#).

The ORR is defined as the proportion of patients with a best response meeting the overall response criteria assessment of CR or PR at any post-baseline response assessment.

If a treated patient is lost to follow up without response assessment, this patient will be counted as a non-responder. Any response on and after new systemic cGVHD treatment will be censored as non-response.

Table 1: cGVHD Response Definitions

| Response | Definition |
|------------------------|---|
| Complete Response (CR) | Resolution of all manifestations of cGVHD in each organ or site. |
| Partial Response (PR) | Improvement in at least one organ or site without progression in any other organ or site. |
| Lack of Response (LR) | |
| Mixed (LR-M) | Complete or partial response in at least one organ accompanied by progression in another organ* |
| Unchanged (LR-U) | Outcomes that do not meet the criteria for complete response, partial response, progression or mixed response |
| Progression (LR-P) | Progression in at least one organ or site without a response in any other organ or site |

* Considered progression for the purposes of analysis

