Response assessment by physician for the nine individual organs (skin, eyes, mouth, esophagus, upper GI, lower GI, liver, lungs and joints and fascia) plus global severity rating will be collected in eCRF.

Time to Response (TTR)

TTR is defined as the time from first treatment to the time of first documentation of response.

Time to Next Therapy (TTNT)

TTNT is defined as the time from first treatment to the time of new systemic cGVHD treatment, censored by last response assessment or long term follow up assessment, which ever is the latest and available.

Corticosteroid Dose

Corticosteroid doses will be presented as mg/kg/day prednisone equivalent dose. If a patient is not using prednisone as the systemic corticosteroid, then the prednisone dose equivalent will be determined according to following conversion ratios:

1mg prednisone is equivalent to:

- 4mg Hydrocortisone
- 0.8mg Methylprednisolone
- 0.15mg Dexamethasone

- 1mg Prednisolone
- 0.8mg Triamcinolone

Transient increase in corticosteroid dosing (not exceeding 1mg/kg/day prednisone equivalent) is permitted for the treatment of cGVHD flare, but dose must be reduced back to the pre-enrollment dose within 6 weeks. If the dose remains elevated for more than 6 weeks, this will be considered a BN101/belumosudil treatment failure. More than 2 episodes of cGVHD flare requiring increased corticosteroid in the first month of BN101/belumosudil treatment will also be considered a BN101/belumosudil treatment failure.

Calcineurin Inhibitor (CNI) Dose

CNI includes systemic tacrolimus and cyclosporine.

Failure Free Survival (FFS)

FFS is defined as the absence of new cGVHD systemic therapy, non-relapse mortality and recurrent malignancy (e.g. underlying disease) and is censored by last response assessment or long term follow up assessment, whichever is the latest and available.

Overall Survival (OS)

OS is defined as time from first dose of BN101/belumosudil to the date of death due to any cause.

Change in cGVHD severity using the Clinician-Reported Global cGVHD Activity Assessment

The Clinician-reported global cGVHD Activity Assessment is a 0-10 point numeric rating scale with a score 0 indicating “cGVHD symptoms not at all severe” and a score of 10 being “most severe cGVHD symptoms possible”. The activities are assessed on Day 1 of each cycle from Cycle 1 Day 1 to EOT.

Change in symptom activity using the cGVHD Activity Assessment Patient Self-Report

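### The SAP's primary ORR omits the protocol rule that response assessments made during a treated cGVHD episode are left out of the primary efficacy analysis

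*SAP*

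**What the plan says.** SAP 8.4.1 takes as the ORR numerator "the number of patients with a best response meeting the criteria of CR or PR at any post-baseline response assessment", divided by the size of the analysis set, for both mITT and PPS. SAP 5.1.1 defines the endpoint in the same way and adds two handling rules. A treated patient lost to follow-up with no response assessment is a non-responder, and "Any response on and after new systemic cGVHD treatment will be censored as non-response".

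Protocol 6.4.1 permits a temporary steroid increase during a cGVHD episode. It then says of a planned response assessment falling in such an episode: "this response assessment will still be performed as planned, but the assessment will not be included in the primary efficacy analysis".

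Two places restate the steroid provisions without that sentence:
- SAP 5.1.2, under Corticosteroid Dose: "Transient increase in corticosteroid dosing (not exceeding 1mg/kg/day prednisone equivalent) is permitted for the treatment of cGVHD flare".
- The protocol synopsis, under concomitant medication: "If the dose remained elevated for more than 6 weeks, it was considered a BN101/belumosudil treatment failure".

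The protocol's general definitions of the endpoint are also silent on it. Section 4.1 has "ORR, defined as the proportion of subjects evaluated as CR or PR according to the NIH Consensus Criteria (2014) at any one post-baseline assessment", and 10.6.2.1 uses the same definition.

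**The concern.** A permitted steroid increase for a flare is not a new systemic cGVHD therapy, so the SAP's one assessment-level exclusion does not cover it. A programmer working from the SAP would let a CR or PR recorded under temporarily raised steroids make a patient a responder, although 6.4.1 keeps that assessment out of the primary analysis.

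The direction is fixed. For an endpoint met at any single visit, admitting more visits can add responders but never remove them.

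The stake is limited. SAP section 6 rules out hypothesis testing, and there is no ORR threshold to cross. In a descriptive study, however, the point estimate and its interval are the result. Protocol 10.1 and SAP section 2 both place finalisation of the SAP before database lock. Deciding afterwards which visits count would be a choice about the primary endpoint made with the responses in view.

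**Working it through.** **1. Is the rule anywhere in the SAP?**

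| Place | Handling of assessments in a treated episode |
|---|---|
| Protocol 6.4.1 | Performed, but not in the primary efficacy analysis |
| Protocol synopsis, 4.1, 10.6.2.1 | Silent |
| SAP 5.1.1 and 8.4.1 (primary ORR) | Silent; any post-baseline assessment counts |
| SAP 5.1.2 (steroid dose) | Flare text repeated, exclusion absent |
| SAP 7 (responder population) | Silent; any post-baseline assessment counts |
| SAP 8.2.1 (missing data) | Silent |
| SAP 8.4.2 (DoR censoring, steroid analyses) | Silent |

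The general definitions neither repeat nor revoke 6.4.1. The specific rule therefore stands, and the SAP does not implement it.

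**2. Interval method.** No figure in the plan depends on this rule, so there is none to reproduce for it. The exact method can be checked on the KD025-213 results in protocol 1.4.2. Clopper-Pearson limits are the 0.025 quantile of Beta(x, n − x + 1) and the 0.975 quantile of Beta(x + 1, n − x).
- 48/66 = 72.7% (60.4 to 83.0)
- 49/66 = 74.2% (62.0 to 84.2)
- 97/132 = 73.5% (65.1 to 80.8)

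All three match the protocol.

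**3. Size per patient.** With the planned N = 30, one patient whose only CR or PR falls in a treated episode adds 1/30 = 3.3 points, and two add 2/30 = 6.7. If the analysis set were 27 (an assumption, for example for PPS), one adds 1/27 = 3.7. The number of such patients cannot be derived from the documents. Over an assumed range of 0, 1 or 2, the shift is 0, +3.3 or +6.7 points.

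One such patient, at three assumed base rates:

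| Barred visits excluded | Barred visits counted | Shift in lower limit |
|---|---|---|
| 15/30 = 50.0% (31.3 to 68.7) | 16/30 = 53.3% (34.3 to 71.7) | 3.0 |
| 20/30 = 66.7% (47.2 to 82.7) | 21/30 = 70.0% (50.6 to 85.3) | 3.4 |
| 25/30 = 83.3% (65.3 to 94.4) | 26/30 = 86.7% (69.3 to 96.2) | 4.0 |

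These intervals are about 27 to 37 points wide, so the shift is small against sampling error.

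**4. How many visits could be barred in one patient?** Assessments up to Cycle 7 fall on Day 1 of Cycles 2, 3, 4, 5 and 7, that is, study days 29, 57, 85, 113 and 169 (28-day cycles, window ±3 days). Protocol 6.4.1 allows a flare dose for up to 6 weeks (42 days). It classes as treatment failure "The occurrence of more than 2 episodes of cGVHD requiring an increase in corticosteroid dose during the first 6 months", so two such episodes are possible without failure. Three consecutive assessments span at least 56 − 6 = 50 days, which exceeds 42, so one course covers at most 2 assessments and two separate courses at most 4 of the 5. This is an upper bound for patients without treatment failure up to Cycle 7 Day 1, not an expected effect. (SAP 5.1.2 gives the episode window as one month rather than six; the two passages must be reconciled. The protocol's figure is used here.)

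A patient with a CR or PR at any visit outside a treated episode is unaffected.

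**The case against.** The strongest reply is that the conflict starts inside the protocol. The SAP carries forward the definition in protocol 10.6.2.1 almost unchanged, the exclusion sits in a concomitant-medication section, and no text says which governs. This stands in part: the protocol sections must be reconciled as well. It does not rescue the SAP. Section 6.4.1 names the primary efficacy analysis explicitly, and if the general wording were meant to prevail, the protocol would contradict itself on its primary endpoint. Either way, a written resolution is needed.

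Second, the bound in step 4 is not a bound for every patient. A dose raised for longer than 6 weeks, or a third episode, is labelled treatment failure, yet neither document removes that patient from the ORR. A 57-day elevation (days 29 to 85) would cover three visits. That is correct, and it is why the bound is restricted to patients without treatment failure.

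Third, the effect may be zero and no decision depends on it. Both are true, and they limit the weight of the point. They do not make the derivation conform to 6.4.1.

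Fourth, 6.4.1 mentions only the primary analysis, so the questions below about TTR and DoR are follow-on specification rather than contradictions. That is fair.

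**Conclusion.** The concern holds. The omission is certain from the text; whether it changes the reported ORR is unknown. Any effect is upward, at 3.3 points per affected patient with N = 30, and the number affected may be zero. The 0-to-2 range and the base rates above are assumptions. No hypothesis test or threshold is at stake, and nothing is claimed about the comparison with KD025-213. The point should be fixed before database lock because it concerns which visits define the primary endpoint.

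**What to change.** 1. Reconcile protocol 4.1 and 10.6.2.1 with 6.4.1, so that the primary endpoint has one definition.
2. Add to SAP 5.1.1 and 8.4.1: *Assessments falling during corticosteroid treatment of a cGVHD flare are excluded when deriving best response for the primary ORR (mITT and PPS). A patient with no CR or PR outside such periods is a non-responder.* Section 6.4.1 does not state the second sentence; it is the convention needed to keep the denominator intact.
3. Define the start and end of a flare-treatment period, for this analysis flag only, from the recorded steroid doses. The only dose benchmark in 6.4.1 is the pre-enrolment level, and after at least 2 weeks on study drug "the dose of corticosteroids may be reduced at the discretion of the investigator". The SAP should therefore say whether an increase from a tapered dose that stays at or below the pre-enrolment level counts.
4. Confirm the periods at data review without reference to response data.
5. Report the ORR with all assessments as a sensitivity analysis.
6. State whether the responder population, TTR and DoR use the same responder status. If so, state how excluded visits are treated for the end of DoR, for the summed episodes of the quaternary DoR, and under the SAP Table 2 rule on two or more missed assessments.

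The cost is two SAP sentences, a period definition, a derived flag, a data-review step and one extra ORR row, plus the protocol reconciliation. Protocol Appendix 1 already has steroid doses collected from consent to 28 days after the last dose. The documents do not show whether the eCRF links a dose increase to a cGVHD episode; if it does not, the data-review step will take more work. The reported ORR may be slightly lower.

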8.4.2. Analyses for Secondary Endpoints

DoR

DoR will be analysed only based on responder population. Kaplan-Meier plots and descriptive statistics of DoR will be provided. The censoring rules in [Table 2](#) will be applied. Landmark analyses with number and percentage of patients with response sustained for ≥ 12 , ≥ 16 , ≥ 20 , ≥ 24 , ≥ 32 , ≥ 40 and ≥ 48 weeks will be provided.

Table 2 Censoring Rules for Duration of Response

| DoR | Events | Censoring |
|------------|--|--|
| Primary | 
 • Deterioration from best response • Initiation of new systemic therapy for cGVHD • Death 
If deterioration from best response or initiation of new systemic therapy happens immediately after two or more missed response assessments, the event date should be set as four weeks (one cycle) after last documented response assessment prior this event.
 | Last documented response assessment |
| Secondary | 
 • Documented LR • Initiation of new systemic therapy for cGVHD • Death 
If LR or initiation of new systemic therapy happens immediately after two or more missed response assessments, the event date should be set as four weeks (one cycle) after last documented response assessment prior this event.
 | |
| Tertiary | 
 • Initiation of new systemic therapy for cGVHD • Death | Last response assessment or long term follow up assessment, whichever is the latest and available. |
| Quaternary | 
 • LR • Initiation of new systemic therapy for cGVHD • Death 
With summation of DoR from multiple episodes.
 | Same with censoring rule for primary and secondary. |

Lee Symptom Scale Score (LSS)

The analyses will be performed based on mITT, responder and nonresponder population. The analyses will include:

- Both scores and change from baseline values (summary score and domain scores) will be summarized as continuous variables by visit.
- Number and percent of patients with a ≥ 7 point reduction (7-PtR) from baseline.

- Number and percent of patients with a 7-PtR from baseline on 2 consecutive assessments.
- Duration of a 7-PtR (DO7-PtR) (defined as time from documentation of the first \geq 7-point resolution to the first documentation of less than 7-point reduction). If there are multiple episodes, the DO7-PtR will be measured as the sum of DO7-PtR from all episodes.

Response by Organ System

The best response (CR, PR) for the nine individual organs plus global severity rating will be summarized. Time to response at the organ level will also be evaluated. Descriptive statistics and plots of cumulative number and percentage of responders over time will be provided. Two series of percentages will be presented:

- With total number of patients in mITT with involvement of the given organ at baseline as denominator
- With numbers of patients in the responder population with involvement of the given organ at baseline as denominator

Time to Response (TTR)

Descriptive statistics and plots of cumulative number and percent of responders over time will be provided. TTR analyses will only be conducted for the responder population.

Time to Next Therapy (TTNT)

TTNT will be analysed by the Kaplan-Meier survival method as well as the landmark analysis at 3, 6, 9, and 12 months.

Corticosteroid Dose

Corticosteroid doses will be presented as prednisone equivalent dose. Descriptive statistics for the mITT population, responder / nonresponder populations will be provided for:

- Systemic corticosteroid dose over time
- Change and percent change from baseline (C1D1) to the greatest corticosteroid dose reduction during BN101/belumosudil treatment period
- Number and percentage of patients who reduced systemic corticosteroid dose during BN101/belumosudil treatment period
- Number and percentage of patients who ever discontinued systemic corticosteroid usage for over 28 days during BN101/belumosudil treatment period

The above analyses will be censored on or after new systemic cGVHD treatment.

Calcineurin Inhibitor (CNI) Dose

CNI includes systemic tacrolimus and cyclosporine. Descriptive statistics will be provided for:

- Number and percentage of patients who reduced CNI dose during BN101/belumosudil treatment period
- Number and percentage of patients who ever discontinued CNI during BN101/belumosudil treatment period

Failure Free Survival (FFS)

Kaplan-Meier plots, descriptive statistics of FFS and landmark FFS at 3, 6, 9, and 12 months will be provided. In addition, analyses for the three components of FFS will also be provided.

Overall Survival (OS)

Kaplan-Meier plots, descriptive statistics of OS and landmark OS at 3, 6, 9, and 12 months will be provided.

Change in cGVHD severity using the Clinician-Reported Global cGVHD Activity Assessment

Change from baseline in cGVHD severity based on the Clinician-reported global cGVHD Activity Assessment will be summarized as a categorical endpoint at all scheduled assessment visits.

Change in symptom activity using the cGVHD Activity Assessment Patient Self-Report

Changes in cGVHD symptoms based on global cGVHD Activity Assessment by the Patient Self-Report will be summarized as a continuous endpoint at all scheduled assessment visits. Both scores as well as the change-from-baseline values will be presented.

The summary of the change-from-baseline of Global Severity Rating on categorical status and the summary of comparison of cGVHD to a month ago will also be presented.

The number and percentage of patients reporting none, mild, moderate, and severe cGVHD will be summarized by visit.

